High vs low urine output targets in elective surgical patients: a randomised controlled safety trial

Study Protocol 13 June 2011

[name], Senior Lecturer, Department of Surgery, University of Auckland

[name], Professor, Christchurch Kidney Research Group, Department of Medicine, University of Otago, Christchurch

[name], Research Fellow, Christchurch Kidney Research Group, Department of Medicine, University of Otago, Christchurch

[name], Senior Lecturer, Christchurch Kidney Research Group, Department of Medicine, University of Otago, Christchurch

[name], Consultant Nephrologist, Department of Medicine, North Shore Hospital, Auckland

[name] Consultant Anaesthetist, Department of Anaesthesiology and Perioperative Medicine, North Shore Hospital, Auckland

[name], Professor, Department of Surgery, University of Otago, Dunedin

[name], Research Fellow, Department of Surgery, University of Auckland

Background

A urine output (UO) below 0.5 ml/kg/h is routinely observed in otherwise well patients undergoing major surgery. This is traditionally regarded as a sign of impending acute kidney injury (AKI) and is therefore treated by liberal fluid infusion. However, several recent studies of perioperative renal function have shown no association between UO and AKI. For example, in a study of 15,102 patients undergoing non-cardiac surgery, intra-operative UO had no correlation to the development of perioperative AKI. In fact, it has long been known that oliguria is an important physiological response to injury, preserving sodium and water in recovering organisms. This response is mediated by antidiuretic hormone release, renin-angiotensin II-aldosterone activation and increased sympathetic nerve action on tubular cells in the nephron.

The current practice of maintaining a high UO in otherwise well patients by liberal fluid infusions can be therefore be questioned. More importantly, a series of recent randomised clinical trials demonstrate that liberal fluid therapy approximately doubles postoperative complication rates as compared to a more restricted fluid regime, confirming findings in animal studies of numerous detrimental effects of perioperative fluid overloading. Three clinical trials demonstrate a relative reduction of 46%, 45% and 84% of overall postoperative morbidity with restricted fluid therapy, clearly identifying fluid overloading as a major, iatrogenic and preventable cause of complications in contemporary surgical care. The main obstacle to fluid restriction in practice is maintaining the traditional high UO target. This study therefore aims to demonstrate that a lower UO target is not associated with renal impairment, confirming previous observational studies.

Aims

This study tests the hypothesis that a urine output target lower than the traditional 0.5 ml/kg/h (0.2 ml/kg/h) does not cause harm to the kidneys. Harm is defined in the widest sense of the word in order to detect any degree of harm. It is therefore evaluated by several highly sensitive methodologies beyond the routinely used serum concentrations of creatinine and urea. These methods include frequent sampling for novel, validated biomarkers of renal stress (neutrophil gelatinase-associated lipocalin (NGAL) and Cystatin C) in combination with renal clearance studies to directly measure renal plasma flow (para-aminohippurate (PAH) clearance) and glomerular filtration rates (Sinistrin clearance).

Importance

Approximately 45% of people in the industrialised world have abdominal surgery during their lifetime. Despite recent significant advances, such as minimally invasive surgery and enhanced-recovery protocols, people undergoing colorectal surgery still have a 35-55% risk of complications. As summarised above, recent trials have identified fluid overloading as a major, iatrogenic and preventable cause of complications in contemporary surgical care. The main cause of fluid overloading is the traditional emphasis on maintaining a high UO. This trial challenges this tradition by evaluating the non-inferiority of a lower UO target, with the ultimate goal of reducing the need for routine aggressive fluid resuscitation in elective surgery and the excess morbidity associated with such fluid excess. The potential impact on the practice and outcomes of surgery across most specialties is therefore large. In addition, this study will elucidate the regulators of renal function in contemporary surgical care, specifically evaluating the respective roles of renal perfusion changes vs changes in renoregulatory hormones.

Table 1. Standardised fluid therapy in ERAS protocol		
Day of surgery	Preop	≥400 ml clear liquids PO Oral bowel preparation not routinely used
	Intraop	5 ml/kg/h Plasma-Lyte 148 IV
		5 ml/kg/h Gelofusine IV
	Postop	0.5 ml/kg/h dextrose-saline IV
		600 ml liquids PO
Total	Approx 2500 ml IV + 1000 ml PO	
POD 1		IV fluids stopped at 8 am
		1500 ml liquids (and standard diet) PO
		If oral intake <800 ml by 6 pm, maintenance infusion of IV dextrose-saline with 20 mmol K/l restarted at 1 ml/kg/h
		In case of vomiting, replacement 1:1 with IV saline 0.9% with 20 mmol K/l is started
		If Hgb <80: Transfuse 2U RBCs If Hgb 80-100: Transfuse 2U RBCs only if symptomatic or ischaemic heart disease or evidence of ongoing bleeding

Study design

This is a prospective randomised assessor-blinded non-inferiority trial. Forty patients undergoing elective bowel surgery will be studied.

Patients with known risk factors for AKI will be excluded.

Baseline measures of effective renal plasma flow (ERPF), glomerular filtration rate (GFR), AKI biomarkers, plasma creatinine and renoregulatory hormones are obtained prior to surgery. Participants are randomised to the Low (0.2 ml/kg/h) or High (0.5 ml/kg/h) groups on induction of general anaesthesia. Randomisation is stratified by baseline renal function. Surgical techniques are per surgeon preference. Perioperative care is standardised according to the North Shore Hospital (NSH) enhanced-recovery after surgery (ERAS) protocol to minimise variation in ancillary care. This includes routine usage of epidural analgesia, routine urinary catheterisation until morning of postoperative day (POD) 2 and a standardised perioperative fluid protocol (see Table 1). During surgery and the next 48 hours, UO is monitored hourly. In both groups, an hourly UO <0.5 ml/kg/h prompts immediate anaesthetic or surgical team review to rule out evidence of potential hypoperfusion of any aetiology (see Figure 1). If this is not present, patients in the High group will receive 500-ml fluid boluses (Plasma-Lyte 148) until UO exceeds 0.5 ml/kg/h. In the Low group, fluid boluses will be only given if UO falls below 0.2 ml/kg/h.

The main endpoint is the urinary NGAL on POD 1. Neutrophil gelatinase-associated lipoprotein, the best-validated and most sensitive biomarker of AKI, will be followed 12-hourly during 48 hours. In addition, plasma cystatin C and creatinine concentrations, urinary electrolytes and osmolality will be measured several times per day, and the ERPF and GFR measurements will be repeated on POD 1. Renoregulatory hormones will also be followed. The study nephrologist will acutely assess any participant with a persistently

Table 2. Exclusion criteria
Preexisting moderate or severe chronic kidney disease (eGFR <60 ml/min/1.73 m ²)
Pre-existing kidney damage regardless of eGFR (single functional kidney, renal transplant, significant proteinuria)
History of previous AKI due to any cause (AKI Network Stage 2)
Need for ongoing angiotensin-converting enzyme inhibitors, angiotensin receptor blockers or non-steroidal anti-inflammatory drugs (NSAIDs)
Nephrotoxic substance administration (including systemic radiocontrast dyes, aminoglycosides, glycopeptides and NSAIDs other than aspirin) within 48 h prior to surgery
Pre-existing hepatic failure (Child-Pugh Score >6)
ASA class IV
Morbid obesity (BMI>35)
Intraoperative ureteric injury
Intraoperative haemorrhage >50% of blood volume
Pregnant or lactating females

low UO despite a total bolus volume of 2 l or a plasma creatinine increase by ≥ 2 -fold compared to baseline at any point. Clinical outcomes will also be recorded.

Participants

Forty men and women aged between 18 and 85 years of age, able to give informed consent, undergoing elective segmental colectomy for benign or malignant disease, by laparotomy or laparoscopy will be studied. Participants will be recruited among patients undergoing bowel surgery at North Shore Hospital. Exclusion criteria are listed in Table 2.

Step-by-step protocol

Recruitment: With the permission of the potential participant, a research fellow or research nurse gives a brief oral and written (Participant's Information Sheet) information about the study in outpatients clinic. The research fellow or research nurse telephones the potential participant 3-7 days later to further discuss the study and seek oral consent. If consent is given, patient attends a separate research visit approximately one week prior to surgery, where written consent is obtained prior to any test procedures.

Preoperative research outpatients visit: Baseline renal function measures will be performed on a dedicated research visit to outpatients clinic approximately one week prior to surgery. Patients present at 9 am overnight fasted. Two IV cannulas are placed. A 3-hour intravenous infusions of sinistrin and PAH is given with the participant resting in a reclining armchair (see Clearance Studies protocol). One urine sample and three blood samples will be taken on this occasion for baseline measures of urinary NGAL, plasma creatinine, cystatin C, electrolytes, osmolality, C-reactive protein (CRP), glucose, and renoregulatory hormones. Plasma concentrations of sinistrin and PAH are determined for calculation of ERPF and GFR. Body composition will be estimated using bioimpedance analysis (BIA).

Randomisation: Participants are randomised (allocation concealment by off-site computer randomisation, The University of Auckland) to the Low or the High group on induction of general anaesthesia.

Study period: The data collection period starts before surgery and ends on POD 30.

Study intervention: The only difference between the two study groups is the response to urine output below 0.5 ml/kg/min from start of anaesthesia until 8am on POD 1 (see Figure 1).

Urinary output is followed hourly. All anaesthetic and surgical teams providing care for participants will be educated face-to-face about the details of the fluid protocols. A research fellow will monitor compliance with protocols around the clock in person and over the phone.

Participants with epidural-related hypotension will follow the standard ERAS protocol (a combination of fluid boluses and reduced epidural infusion rates).

Participants with complications remain in the study. As per the study fluid algorithms (Figure 1), the UO target in the Low group will switch from 0.2 to 0.5 ml/kg/h if there are any signs of hypoperfusion.

At the routine 30-day outpatients clinic followup, a final urine and plasma sample will be collected.

Nephrologist review triggers: The on-site study nephrologist [name] (or a named colleague in his absence) will urgently (within 12 hours) review any participant with an absent UO response to a 2L fluid bolus (see Figure 2), or with AKI Network (AKIN) stage 2 AKI per creatinine criteria (persistent elevations of plasma creatinine $\geq 100\%$ above baseline despite adequate fluid resuscitation) within 30 days, and institute adequate therapy.

Independent Monitoring Committee: Two independent senior consultant nephrologists ([name] at Auckland City Hospital and [name] at Middlemore Hospital) make up an independent Monitoring Committee, which will review individual clinical outcomes as well as postoperative changes in plasma creatinine in all participants after completion of four and 20 participants.

Study halt triggers: In addition, the study will be halted pending urgent review by the independent Monitoring Committee if the following occurs: Two or more participants in the intervention arm develop AKI Network (AKIN) stage 3 AKI per creatinine criteria (persistent elevations of plasma creatinine $\geq 200\%$ above baseline despite adequate fluid resuscitation) within seven days after surgery and in the absence of a clear-cut alternative cause (such as major systemic complication of surgery).

Table 3. Secondary endpoints
Urinary excretion of NGAL 0800 POD1 - 0800 POD 2 and total excretion during intervention period
Urinary concentrations of NGAL and creatinine and osmolality during and after surgery
Plasma concentrations of cystatin C, creatinine, ADH, aldosterone, renin and angiotensin II and osmolality during and after surgery
ERPF and GFR before and 1 day after surgery
30-day incidence of complications (including AKI) classified and defined as per Auckland ERAS database, graded per Clavien-Dindo grading scale
Length of stay, time to repeated flatus
IV and oral fluid volumes and changes in body weight and lean tissue mass (BIA)

Depending on the findings of the independent Monitoring Committee, the study may then close or resume with changes as recommended.

Endpoints

The primary endpoint is urinary concentration of NGAL at 2 pm on POD 1. Secondary endpoints are listed in Table 3.

Urine samples are collected once at the preoperative research visit and at regular intervals during and 72 hours after surgery and once on POD 30 (See further Blood and urine sampling protocol).

Plasma samples are collected three times at the preoperative research visit, at regular intervals during and 72 hours after surgery and once on POD 30. In addition, two more samples are taken when the sinistrin-PAH test is repeated 0800-1100 on POD 1 (See further Blood and urine sampling protocol).

Clinical data including demographics, diagnosis, surgery, anaesthesia, complications and recovery parameters are prospectively collected as per standard practice by an ERAS Nurse Specialist in the Auckland ERAS database.

Sample handling and analysis

A research fellow or a research nurse will collect all samples. Some assays will be performed on collection by Waitemata DHB Laboratories; others will be stored in a dedicated -80°C alarmed research freezer at Waitemata DHB Laboratories for later batch analyses by the Christchurch co-investigators. All assays will be performed by staff unaware of participants' group allocation.

Statistical considerations

On the basis of a recent study in surgical trauma, the mean (SD) urinary NGAL concentration at 2pm on the first postoperative day in the control (High) group is assumed to be 10 (10) ng/ml, and the clinically significant cut-off in the Low group is assumed to be 25 ng/ml. To show non-inferiority with 90% power, a minimum of 18 participants completing the study per treatment group will be needed based on a margin of non-inferiority of 15 µg/L (25-10 ng/ml), a common SD of 15 ng/ml, and 0.05 one-sided significance level. Assuming 10% dropout, 20 participants per treatment group will be recruited (40 participants in total).

Certain data indicate that urinary NGAL follows a log-normal distribution. To ensure this will not increase the sample size required, a sample size calculation taking this into account

has also been performed. This indicates that a minimum of 31 participants, 15.3 in each treatment arm, will be needed based on a margin of non-inferiority of log 15 ng/ml and an SD of log 10 ng/ml, with 90% power using a one-sided statistical test with an alpha level of 0.05. A sample size of 40 patients will therefore be sufficient should urinary NGAL be log-normally distributed in the planned study. This sample size calculation was performed with the assistance of [name], Waitemata DHB statistician.

Repeated measures will be analysed by analyses of variance for repeated measures (time x treatment group with post-hoc Tukey's test as appropriate) or mixed regression models if appropriate. Student's unpaired t-test or, if non-normally distributed, Mann-Whitney U test and Fisher's exact test will be used as appropriate.

Planned subgroup analysis are: moderate vs no chronic kidney disease, patients with vs without epidural analgesia, patients undergoing surgery via laparotomy vs laparoscopy.

Appendices

1. Blood and urine sampling protocol
2. Clearance studies protocol

References

Sweny P. Is postoperative oliguria avoidable? *Br J Anaesth*. 1991;67:137-145.

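### The two-group tests named for a single-time-point endpoint use neither the randomisation stratum nor baseline urinary NGAL, so an almost free gain in precision is missed

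*Protocol*

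**What the plan says.** Four places in the protocol bear on this.

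- **Study design:** "Randomisation is stratified by baseline renal function". The variable and cut-point are not given there.
- **Step-by-step protocol, preoperative research outpatients visit:** about a week before surgery, "One urine sample and three blood samples will be taken on this occasion for baseline measures of urinary NGAL" and other analytes. A baseline value of the primary endpoint variable is therefore planned for each participant.
- **Endpoints:** "The primary endpoint is urinary concentration of NGAL at 2 pm on POD 1". This is a single time point.
- **Statistical considerations:** the methods are "Student's unpaired t-test or, if non-normally distributed, Mann-Whitney U test and Fisher's exact test will be used as appropriate". Repeated measures get an analysis of variance by time and treatment group, "or mixed regression models if appropriate". No baseline or stratum term is named in either place. The sample size is an unadjusted comparison of means, with "a common SD of 15 ng/ml, and 0.05 one-sided significance level".

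**The concern.** A trial that stratifies its allocation on a factor, and measures the endpoint variable before treatment, normally uses both in the analysis. If the stratum predicts the outcome, balancing on it and then ignoring it leaves a standard error that is larger than the true sampling variation. If baseline NGAL predicts POD 1 NGAL, an unadjusted comparison leaves that explained variation in the error term. The prognostic part of any chance baseline imbalance also stays in the estimate.

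Non-inferiority is decided by an upper confidence limit. In both cases that limit is wider than it need be, and a trial with about 18 evaluable participants per arm has little room for a larger SD than planned.

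**Working it through.** **Inputs from Statistical considerations:** margin 15 ng/ml (25 − 10), common SD 15 ng/ml, one-sided alpha 0.05, power 90%, 18 evaluable per arm, 10% dropout. The true difference is taken as 0.

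**1. The protocol's own figure.** n per arm = 2 × (1.645 + 1.282)² × (15/15)² = 17.13, so 18. Allowing for dropout, 18/0.9 = 20 per arm, 40 in total. Both figures reproduce with no covariate.

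**2. Unadjusted power.** At 18 per arm the noncentrality is 15 / (15 × √(2/18)) = 3.0. The noncentral t with 34 df gives 90.2%. At 20 per arm the power is 92.8%. The one-sided 95% half-width at 18 per arm is 1.691 × 15 × √(2/18) = 8.45 ng/ml.

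**3. Adjusting for baseline.** Residual SD = 15 × √(1 − r²), so the variance falls by r². The protocol gives no r, so the values below are assumptions. They use the noncentral t with 33 df at 18 per arm; one further df for a two-level stratum changes no power by more than 0.1 percentage point.

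| Assumed r | Fall in residual variance | Power | Half-width (ng/ml) |
|---|---|---|---|
| 0.2 | 4% | 91.2% | 8.29 |
| 0.3 | 9% | 92.4% | 8.07 |
| 0.5 | 25% | 96.0% | 7.33 |
| 0.7 | 49% | 99.3% | 6.04 |

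**4. Cost if the covariates are useless (r = 0).** Going from 34 to 32 df costs under 0.1 percentage point (90.23% to 90.16%). That counts degrees of freedom only. Chance imbalance in an uninformative baseline multiplies the variance of the arm effect by about 1 + 1/31 on average. The noncentrality is then 3.0/√(1 + 1/31) = 2.95, and power is about 89.3%. The whole cost is thus under 1 point. The same allowance takes a little off each power in the table (at r = 0.5, 95.4% by simulation) and puts break-even near r = 0.2.

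**5. Log scale.** Statistical considerations allows that NGAL may be log-normal. Assume a margin of ln(25/10) = ln 2.5 = 0.916 and log SD = √ln(1 + CV²). This margin is an assumption; the protocol's log calculation uses log 15 with an SD of log 10.

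- CV 1.0 (mean 10, SD 10): log SD √ln 2 = 0.833, unadjusted power 94.4%; about 96% at r = 0.3 and 98% at r = 0.5.
- CV 1.5 (mean 10, SD 15): log SD √ln 3.25 = 1.086, unadjusted power 79.8%; 83.0%, 88.8% and 96.6% at r = 0.3, 0.5 and 0.7.

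**6. If the raw SD were 20 (assumption).** Power at 18 per arm is about 71% unadjusted, and 75%, 82% and 92.5% at r = 0.3, 0.5 and 0.7.

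**7. Ignoring the stratum.** With two equal, balanced strata and 18 per arm, simulation of the nominal 5% one-sided t-test gave a rejection rate of 4.1% if the stratum explains 10% of the variance and 2.8% if it explains 25%. The error is on the conservative side.

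**The case against.** The strongest reply is that nothing here is wrong. An unadjusted comparison is valid in a randomised trial, covariates are commonly set in an analysis plan that is not at hand, and the present wording leaves room for them. Tests are to be used as appropriate, mixed models are allowed for repeated measures, and NGAL is measured repeatedly. Most of this stands. The point survives because the protocol is not silent: it names methods, and the one that fits a single-time-point continuous endpoint, "Student's unpaired t-test or, if non-normally distributed, Mann-Whitney U test", has no place for either variable.

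The benefit may also be small. The baseline is one sample taken about a week before major surgery, and excluding eGFR below 60 (Table 2) narrows the stratification factor. A low correlation is plausible, and at 0.2 there is almost nothing to gain. That stands too.

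Three stronger readings are tempting but not supported:

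- **That the trial needs adjustment to reach its power.** It does not: 90.2% is reached without it. The 79.8% log-scale figure depends on pairing the common SD of 15 with the control mean of 10. Using the control SD of 10 gives 94.4%.
- **That ignoring the stratum invalidates the test.** The effect arises only if the stratum is prognostic, and it makes a false claim of non-inferiority less likely.
- **That a baseline imbalance carries over in full.** Only its prognostic part does, and the unadjusted standard error already allows for chance imbalance.

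**Conclusion.** The point holds as a missed efficiency gain. It is neither a validity error nor a power shortfall. It rests on reading the t-test or Mann-Whitney U as the primary comparison; a reader might infer that the protocol commits to this, but it assigns no test to that endpoint.

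The size depends on a correlation that the protocol does not give. On the planned inputs the gain is about 1 to 2 points of power at r = 0.2 to 0.3, about 6 at 0.5 and about 9 at 0.7. It is worth more if variability is larger than planned. The downside with uninformative covariates is under 1 point. The sample size of 40 is unaffected.

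**What to change.** State in Statistical considerations that the primary non-inferiority comparison is an ANCOVA of urinary NGAL at 2 pm on POD 1, on the log scale if log-normality is accepted. The terms are treatment arm, baseline urinary NGAL on the same scale, and the renal-function stratum as used at randomisation. Compare the one-sided 95% upper limit for Low versus High from that model with the margin on the same scale: a difference on the raw scale, a ratio on the log scale. The unadjusted comparison can stay as a sensitivity analysis. Keep 40 participants; the gain should serve as protection against a larger SD and not as a reason to recruit fewer.

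The cost is a change of wording and two degrees of freedom if the stratum has two levels. No new data are needed, since the baseline sample is already planned and the stratum is known at randomisation.

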where I is the infusate concentration, V_i is the infusion volume, P is the arithmetic mean of the plasma concentrations.

Enhancing recovery after surgery

Surgical team protocol: Small bowel and colon surgery

Scope: This clinical pathway outlines the standard care for elective open or laparoscopic small bowel or colon surgery (including high anterior resection without dissection below peritoneal reflection).

Deviations: Protocol deviations are authorised by the patient's surgeon or anaesthetist, and documented by the nurse on the *Care Plan*.

Length of stay: Expected length of postoperative hospital stay is 4 nights.

Before surgery

- Preoperative patient education 1-2 weeks before surgery.
- Bowel preparation according to Departmental *Bowel Preparation Protocol*.
- Same-day admission.
- Normal diet allowed until 6 hours before anaesthesia. Clear oral fluids allowed until 2 hours before anaesthesia.
- Preoperative oral carbohydrate treatment 2 hours before anaesthesia. **Exceptions:** pts with insulin-treated diabetes; pts with signs of gastrointestinal obstruction (bloating, nausea).
- Admitting nurse ensures that time oral carbohydrate is taken is documented on the *How to take your Nutricia PreOp® Drink* form.

Surgery

- Minimally invasive techniques and short incisions are used.
- Abdominal wound drainage is avoided.

Day of surgery

- After surgery, 500 ml dextrose-saline until 8 am POD 1. Diabetics on GIK infusion (approx 80 ml/h) need no other IV fluids.
- Free oral fluids and a sandwich offered 4 h after surgery.
- Postoperative oral fluid intake target: 600 ml (including 400 ml Fortisip).
- Postoperative nutritional target: 2 cartons (400 ml) of Fortisip.

- Urine output target is >0.5 ml/kg/h (for 50 kg patient, 25 ml/h; for 75 kg, 33 ml/h; for 100 kg, 50 ml/h). See *Anaesthetic Team Protocol for poor urine output action plan*.
- Mobilisation target: 2 hours out of bed (in chair or walking).
- Ensure paracetamol and Clexane (8 pm) charted.

Waitemata
District Health Board
Te Wai Awhina

Our core values Customer Focus 'eye' | Integrity 'sunrise' | Compassion 'bird' | Respect 'koru' | Openness 'flower'

Postoperative day 1

- IV infusion stopped at 8 am.
- Check body weight by 10 am.
- Standard (not postoperative) diet.
- Oral fluid intake target: 1500 ml (including 600 ml Fortisip).
- Nutritional target: 3 cartons (600 ml) of Fortisip. Some cooked food.

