- If urine output <0.5 ml/kg/h: 1) examine patient, review fluid balance and fluid status, and contact patient's anaesthetist and surgeon if any signs or symptoms of hypoperfusion (for example, sepsis or heart failure); 2) give 500 ml of Plasma-Lyte 148 IV over 15 min; 3) review urine output over next hour; 4) if urine output still <0.5 ml/kg/h go back to 1) repeating until 2 L Plasma-Lyte 148 has been given; 5) obtain senior review.

Epidural-related symptomatic hypotension in theatre, PACU, HDU:

- 1) Metaraminol infusion per protocol, 2) ephedrine IV if bradycardic, 3) noradrenaline infusion

Epidural-related symptomatic hypotension on ward:

- 1) Review patient and liaise with patient's anaesthetist and surgeon,
- 2) 500 ml of Plasma-Lyte 148 IV over 15 minutes, 3) Stop epidural basal rate,
- 4) 500 ml of Plasma-Lyte 148 IV over 15 minutes, 5) consider other causes

Postoperative multimodal analgesia - *these are prescribed by patient's anaesthetist on day of surgery in theatre:*

From surgery - POD 1 8 am: paracetamol 1g IV (or PO if tolerated) 6-hrly

From POD1 8 am: paracetamol 1g PO 6-hrly

From POD2 8 am - POD7: etoricoxib 60-90 mg PO OD

From POD2 8 am - POD7: tramadol SR 100mg PO 12-hrly

Breakthrough pain:

- 1) Assess epidural function and liaise with patient's anaesthetist,
- 2) Tramadol 50-100mg 6rly PO/IV,
- 3) oxycodone sustained release (Oxycontin) PO 10-20mg PRN,
- 4) oxycodone 0.5-1mg IV PRN

Waitemata
District Health Board
Te Wai Awhina

Our core values | Customer Focus 'eye' | Integrity 'sunrise' | Compassion 'bird' | Respect 'koru' | Openness 'flower'

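### The Study intervention sentence gives the urine output trigger per minute instead of per hour, and the attached ERAS pathways give 33 ml/h for 0.5 ml/kg/h at 75 kg (correct: 37.5 ml/h)

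*Protocol*

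**What the plan says.** **Trigger for action.** Under Step-by-step protocol, the Study intervention paragraph describes the sole difference between the groups as "the response to urine output below 0.5 ml/kg/min from start of anaesthesia until 8am on POD 1", and refers to Figure 1 for the algorithm.

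The other sections of the protocol state the threshold per hour:

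- Aims: "a urine output target lower than the traditional 0.5 ml/kg/h (0.2 ml/kg/h) does not cause harm to the kidneys".
- Study design, groups: "Participants are randomised to the Low (0.2 ml/kg/h) or High (0.5 ml/kg/h) groups on induction of general anaesthesia".
- Study design, review rule: "In both groups, an hourly UO <0.5 ml/kg/h prompts immediate anaesthetic or surgical team review". The same section gives the bolus rules: 500 ml boluses in the High group until output exceeds 0.5 ml/kg/h, and boluses in the Low group only below 0.2 ml/kg/h.
- Step-by-step protocol, on complications: "the UO target in the Low group will switch from 0.2 to 0.5 ml/kg/h if there are any signs of hypoperfusion".

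**Bedside conversion.** Study design makes the hospital's ERAS protocol the standard perioperative care for the trial, and the pathways are attached. The surgical team pathway states, for the day of surgery and again for postoperative day 1: "Urine output target is >0.5 ml/kg/h (for 50 kg patient, 25 ml/h; for 75 kg, 33 ml/h; for 100 kg, 50 ml/h". The anaesthetic team pathway, under Urine output, has the same three examples, including "for 75 kg, 33 ml/h; for 100 kg, 50 ml/h". Its action plan for poor output is given only per kilogram and hour: "If urine output <0.5 ml/kg/h: 1) examine patient, review fluid balance and fluid status".

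**The concern.** The trial randomises patients to two responses to low urine output, so the output that triggers a response is part of the treatment definition. Two of the printed values are wrong.

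The first is a unit error in the sentence that sums up the contrast between the groups. It contradicts the rest of the protocol.

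The second is an arithmetic error in an example written for the teams who will act on hourly output. A nurse or doctor who takes 33 ml/h as the limit for a patient of about 75 kg would regard an hour with, say, 35 ml as on target, although it is below 0.5 ml/kg/h. The review owed to patients in both groups would not happen. In the High group, during the intervention period, the bolus would not be given either. The pathways print no volume example for the Low group's 0.2 ml/kg/h, so an error of this kind would lower the bolus threshold in the High group only and bring the groups slightly closer together.

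**Working it through.** **Inputs**

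- Threshold in the Study intervention paragraph: 0.5 ml/kg/min.
- Threshold in Background, Aims, Study design and the ERAS pathways: 0.5 ml/kg/h.
- Low group threshold (Study design): 0.2 ml/kg/h.
- Pathway examples: 25, 33 and 50 ml/h for 50, 75 and 100 kg.
- Bolus in the High group (Study design): 500 ml.

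**Step 1: reproduce the pathway examples.** Hourly volume = 0.5 ml/kg/h × weight.

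| Weight | Printed | 0.5 × weight | Printed volume ÷ weight |
|---|---|---|---|
| 50 kg | 25 ml/h | 25 ml/h | 0.50 ml/kg/h |
| 75 kg | 33 ml/h | 37.5 ml/h | 0.44 ml/kg/h |
| 100 kg | 50 ml/h | 50 ml/h | 0.50 ml/kg/h |

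The outer two reproduce exactly and the middle one does not. The shortfall is 37.5 − 33 = 4.5 ml/h, and 4.5 / 37.5 = 12%. The weight for which 33 ml/h would be correct is 33 / 0.5 = 66 kg. Rounding does not explain the gap. The same value stands in three places beside correct neighbours, so a fault in reading the PDF is unlikely.

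**Step 2: convert the per-minute figure.** 0.5 ml/kg/min × 60 min/h = 30 ml/kg/h. The ratio to the intended value is 30 / 0.5 = 60. At 75 kg it is 30 × 75 = 2,250 ml/h, against 37.5 ml/h intended.

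**Step 3: what follows if 33 ml/h is used at 75 kg.**

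- Affected outputs: 33 to just under 37.5 ml/h, that is 0.44 to 0.50 ml/kg/h.
- Per affected hourly reading: 0 to 1 missed review in either group, and 0 to 500 ml of bolus not given in the High group up to 8 am on postoperative day 1. All are 0 if staff calculate from body weight.
- Separation of the bolus thresholds: the Low threshold is 0.2 × 75 = 15 ml/h. The intended gap is 37.5 − 15 = 22.5 ml/h; with the printed figure it is 33 − 15 = 18 ml/h.

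**Step 4: link to the sample size.** The calculation under Statistical considerations uses a margin of 15 ng/ml, an SD of 15 ng/ml, one-sided alpha of 0.05 and 90% power. No urine output threshold enters it, so neither error changes it.

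**The case against.** The strongest case on the other side is that both are proofreading slips without effect. The per-minute figure is implausible on its face, the paragraph refers to Figure 1 for the algorithm, and Study design sets out the rules for each group with the right unit. The 33 ml/h is one illustration in hospital documents for standard care. The correct rule stands in the same sentence each time, and the action plan uses only ml/kg/h. To do harm, the error needs a patient near 75 kg, an output in a 4.5 ml/h window, and staff who prefer the example to the rule. The protocol also provides face-to-face education and round-the-clock monitoring of compliance. Even with 33 ml/h, the High threshold is more than twice the Low one at 75 kg (33 against 15 ml/h). The postoperative day 1 entry concerns, after 8 am, only the common review and not the difference between groups.

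All of this stands as an argument about weight, and it keeps the point minor. It does not make the text right. The pathways are the trial's standard care by the protocol's own statement, and they address the teams who must respond to low output. The anaesthetic pathway also uses a 75 kg patient as its example for intraoperative fluids, so the wrong figure falls at a weight that staff are likely to look up.

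**Conclusion.** Both errors are confirmed, and both are minor. The per-minute unit is 60 times the intended trigger but will hardly be acted on, because every other statement of the threshold contradicts it. The 33 ml/h example is 12% low at 75 kg. If followed, it costs up to one review per affected hourly reading in either group and up to 500 ml of bolus in the High group until 8 am on postoperative day 1.

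These are upper limits and not estimates. The documents do not say how often staff would use the example, and the figure is zero if they calculate from weight. No bias is shown, and the sample size and margin are unaffected. Figure 1 was not available in the copy reviewed, so its units could not be checked; the conclusion rests on the text alone.

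**What to change.** - In the Study intervention paragraph, change ml/kg/min to ml/kg/h.
- In the surgical team pathway (day of surgery and postoperative day 1) and the anaesthetic team pathway (Urine output), change 33 to 37.5 ml/h for 75 kg.
- While making these changes, confirm that Figure 1 gives the threshold per hour.

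This amounts to one unit and one number printed in three places. It has no cost in data, sample size or timeline.
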